Official Title: Medication Enhanced CM for Cocaine Dependence

NCA Number: 02111798

Document Date: January 2, 2019

Date: January 2, 2019

Principal Investigator: [name].

Application Number: NA00090062

JHM IRB - eForm A - Protocol

• Use the section headings to write the JHM IRB eForm A, inserting the appropriate material in each. If a section is not applicable, leave heading in and insert N/A.

 When submitting JHM IRB eForm A (new or revised), enter the date submitted to the field at the top of JHM IRB eForm A.

1. Abstract

Provide no more than a one page research abstract briefly stating the problem, the research hypothesis, and the importance of the research.

The efficacy of behavior therapies may be enhanced by certain medications, particularly those that act on dopaminergic systems. This project will examine effects of bupropion on initiation and maintenance of cocaine abstinence in a population of cocaine dependent methadone maintenance patients. Bupropion appears to be the most promising medication for this purpose because of its previously demonstrated efficacy and safety as well as its pharmacological actions at dopamine systems.

Methadone maintained cocaine dependent study participants (N = 100) will be stratified according to whether or not they stop their cocaine use during initial exposure to an abstinence incentive (contingency management) procedure and will be randomly assigned to receive bupropion XL (300mg/day) versus placebo for the remainder of the study. Our hypothesis is that bupropion as compared to placebo treatment will both enhance rates of abstinence initiation in those who have difficulty stopping cocaine and retard rates of relapse in those who initially stopped their cocaine use.

Participants will receive a CM schedule that is tailored to their initial CM response and outcomes will be tracked over a 6-month time frame that includes assessment of drug use outcomes after incentives have stopped. In addition, the project will provide novel information about mechanisms of medication effects by measuring subjective drug effects, drug vs money choices, and self-reports of pleasure derived from daily non-drug activities. We hypothesize that bupropion compared to placebo participants will report non-drug activities as more pleasurable (reinforcing), will engage in more of them and that measures of non-drug reinforcement will mediate abstinence outcomes.

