Following completion of the 10 week stable earning phase at \$11 per negative urine, payment escalation reverses and the per urine payment schedule begins to decelerate. Note that the schedule is shown ending at study week 24. However, participants will be enrolled in the study for 30 weeks and allowed to continue earning through week 26. This allows time for those who may qualify later during Lead-In or have brief slips to complete the schedule and also time to track drug use and relapse measures after all reinforcement is withdrawn. Gradual pay reduction schedules have been used successfully in our clinical laboratory as relapse tests in cocaine self-administration (Donny et al., 2003, 2004) and smoking (Juliano et al., 2006) studies. Under this schedule, relapse will be delayed to the extent that the money alternative is perceived as more motivating and/or motivation for abstinence has shifted to reinforcers in the natural environment other than the monetary payments. Thus, bupropion is expected to slow or prevent relapse because the saliency of non-drug reinforcers maintaining abstinence will be enhanced. A maximum total of \$688 can be earned by those who are continuously abstinent with the exception of no more than two single cocaine positive urines.

Abstinence incentive schedule: initially drug-positive.

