The aim of this study is to evaluate whether bupropion will enhance cocaine abstinence among methadone-maintained patients who are abusing cocaine. This is being evaluated in a double-blind context. Further, based on evidence that individuals with cocaine use disorder typically present to the clinic with a urine sample that is positive for cocaine (which predicts continued use) or negative for cocaine (which predicts abstinence), we had originally proposed to treat those individuals as two separate groups and run 2 parallel studies (presented as Primary Aims 1 and 2), using contingency management as a background platform to support either abstinence or relapse prevention, respectively. Each aim was intended to enroll 100 individuals (N=200) total, to enable equal distribution of bupropion (n=50) and placebo (n=50) within each aim.

Based on unanticipated difficulties with recruitment, we are now collapsing the two parallel studies into the same overarching study, such that Primary Aim 1 will now be examining the effects of bupropion XL vs. placebo on 24-week abstinence outcomes during and after exposure to a behavioral intervention (CM). We are reducing our sample size to 100 individuals, which still preserves the required 50 participants per medication group that was identified in our power analyses as necessary to detect an effect of the medication. This approach will allow us to achieve our primary aim of determining whether bupropion will enhance cocaine abstinence despite challenges with recruitment and will enable this study to still provide clinically important information to advance the treatment of cocaine use disorder.

We are modifying our statistical plan to accommodate this change in sample size. We will retain the original primary outcome measure (biochemically-confirmed abstinence from cocaine), which will be assessed across all participants (independent of abstinence group) in the same statistical model. The endpoint will be binary (abstinent yes or no), and the treatment effect will be assessed using a repeated-measures logistic regression model having two main effects: medication and time, plus their interaction, as

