Responsibility for monitoring data and safety during this clinical trial resides with the Principal Investigator (PI) [name] and co-investigator [name], M.D. AE's and SAE's are generally discovered through careful and frequent monitoring of participants by research and clinical staff using open-ended questions about how the participant has been feeling recently. Any complaint is probed for information about frequency, duration and severity, coded on a side-effects checklist and described in a written summary report. The Principal Investigator coordinates the preparation of semi-annual summary reports on the prevalence of side effects and adverse events observed during the course of the study. These reports will be provided annually to the local IRB and to the NIDA Program Official with the annual progress report. The PI will also be responsible for promptly notifying in writing the local Institutional Review Board if a serious adverse event (SAE) occurs. A SAE is defined as either: death; a life-threatening occurrence; hospitalization; new onset significant medical disorder; or significant exacerbation of an existing medical disorder.

In addition an independent panel of consultants will be contracted for bi-annual review of the risks-benefits ratio of the study. At mid-point during enrollment (when 100 randomized participants have completed the study) this panel will be provided with reports of adverse events and with participant outcome data (urine sample results) by unlabeled medication groups (A vs. B), as a function of study assignment (relapse prevention vs abstinence initiation). This information will be used to assess whether the risks reported are considered to be of unusual magnitude or frequency across any specific groups and to determine whether the study should be ended prematurely due to participant safety concerns. It is unlikely that such a small study would be interrupted because of an uneven distribution of adverse events experienced by any one group, however we will ensure that a qualified panel of reviewers makes this decision.

9. Benefits

a. Description of the probable benefits for the participant and for society.

Study participation will directly benefit participants by providing them with methadone maintenance for opioid dependence, with increased urine monitoring beyond that available in usual care and with contingency management that is likely to reduce the amount of cocaine they use.

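### The mid-point safety review still waits for 100 completers, which is now the whole trial, so it comes after the last participant finishes or not at all

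*Combined protocol and SAP*

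**What the plan says.** Section 7, Risks Management, provides for an independent panel of consultants. Besides bi-annual review of risks against benefits, the panel has one specified look at data by arm: "At mid-point during enrollment (when 100 randomized participants have completed the study) this panel will be provided with reports of adverse events". At that look it also receives urine results, by medication group labelled only A and B and by study assignment. One stated use of the information is "to determine whether the study should be ended prematurely due to participant safety concerns".

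Section 6, Sample size and power, describes the superseded design: "Each aim was intended to enroll 100 individuals (N=200) total, to enable equal distribution of bupropion (n=50) and placebo (n=50) within each aim". It then gives the current one: "We are reducing our sample size to 100 individuals, which still preserves the required 50 participants per medication group". The abstract agrees with the current figure: "Methadone maintained cocaine dependent study participants (N = 100) will be stratified" and then randomly assigned.

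On what it takes to complete, Section 4 states that "participants will be enrolled in the study for 30 weeks and allowed to continue earning through week 26".

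**The concern.** A review held once 100 participants have completed cannot be the mid-point of a trial of 100. The count looks like a remnant of the 200-person design that was missed when the sample was cut. It stands in operative text, not in a log of changes, so staff who follow the number will follow the wrong one.

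At stake is the ability to act on an imbalance between arms while participants are still being exposed. The trial is double-blind, and Section 7 names dose-dependent seizures and neuropsychiatric events among the risks of the drug. Section 6 lists early stopping rules as an item to be covered, but the text beneath it states none and describes no interim analysis. No other passage therefore supplies a by-arm look that could lead to early ending.

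**Working it through.** **Inputs from the documents**
- Trigger: 100 randomised participants who have completed, described as the mid-point during enrolment (Section 7, Risks Management).
- Superseded total: 2 aims × 100 = 200 (Section 6).
- Current total: 2 medication groups × 50 = 100 (Section 6; the abstract agrees).
- Duration: 30 weeks (Section 4).

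**Assumption.** The documents give no dropout rate and do not say whether dropouts are replaced. I use a range of 0% to 40%, with participants dropping out independently and no replacement unless stated.

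**Step 1. Reproduce the stated trigger.** Mid-point = planned total / 2.
- Superseded design: 200 / 2 = 100, which matches exactly.
- Current design: 100 / 2 = 50, which does not match.

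As a share of the sample, the trigger was 100/200 = 50% and is now 100/100 = 100%.

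**Step 2. Can the trigger be reached if completed means finishing the 30 weeks?** All 100 must finish. With dropout d, the expected number of completers is 100 × (1 − d) and P(all 100 finish) = (1 − d)^100. The number that would have to be randomised to yield 100 completers is 100 / (1 − d), rounded up.

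| Assumed dropout | Expected completers of 100 | P(all 100 complete) | Randomised needed for 100 completers |
|---|---|---|---|
| 0% | 100 | 100% | 100 |
| 1% | 99 | 36.6% | 102 |
| 5% | 95 | 0.59% | 106 |
| 10% | 90 | 0.003% | 112 |
| 20% | 80 | about 2 × 10⁻¹⁰ | 125 |
| 30% | 70 | about 3 × 10⁻¹⁶ | 143 |
| 40% | 60 | about 7 × 10⁻²³ | 167 |

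Any dropout above zero calls for more randomised participants than the plan allows. The plan itself foresees losses: clinic dismissal, side effects, new medical conditions, pregnancy and the start of excluded medications are all listed as reasons for leaving, and the analysis model was chosen partly to cope with incomplete data.

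**Step 3. If completed only means that participation has ended.** The trigger is then met when the last of the 100 leaves. Participants still to be protected: 100 − 100 = 0.

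**Step 4. Would a trigger of 50 work?** P(at least 50 of 100 complete) is about 1.00 for dropout up to 30% and 0.98 at 40%. A count of 50 completers is reachable across the range. It comes later than mid-enrolment, however: at 20% dropout, 50 / 0.8 = 62.5, so about 63 randomised participants would already have finished or left, and others would be in progress. A count of randomised participants is not delayed by dropout after randomisation.

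**The case against.** The strongest reply is that this is an un-updated number in a parenthesis. The sentence leads with the mid-point of enrolment, and a sensible reader could follow those words and ignore the count. Meanwhile the same panel still reviews risks and benefits twice a year, adverse events are summarised semi-annually, serious events go promptly to the IRB, and emergency unblinding is available at all times. Nothing says that a bi-annual review may not recommend ending the study. A look at 50 participants would also be a weak detector of rare harms. With about 25 on bupropion, the chance of seeing even one event is 1 − (1 − r)^25, which is 2%, 22% or 72% for assumed true rates r of 0.1%, 1% or 5%. The section itself thinks an interruption unlikely in so small a study.

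Much of this stands. Oversight is not absent, individual reporting remains the main protection against rare serious events, and the primary analysis is untouched. The old design should not be flattered either. About 100 participants left to protect at its mid-point is an upper figure that assumes no attrition and no enrolment ahead of completions. At 80% completion, 100 / 0.8 = 125 would already have finished or left, leaving at most 75 of 200.

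It does not rescue the trigger. The parenthesis is how the plan defines the mid-point, so the sentence now gives two incompatible instructions, and the only countable one yields no timely review. The text does not say that the bi-annual reviews receive data by arm; it attaches such data to this look alone. Reports on single cases may not show an imbalance between groups. The remark that interruption is unlikely comes with a commitment that a qualified panel will make that decision, which the panel cannot do once everyone has finished.

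**Conclusion.** The concern holds, and the plan is wrong as written. The trigger equals half of the superseded 200 and the whole of the current 100. Followed literally, the by-arm review takes place when the last participant finishes, or never if anyone drops out and is not replaced. Under the present design, the number of participants it could still protect is 0.

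That conclusion needs no dropout figure. Only the chance of never reaching the trigger depends on the assumed rates, on independence between participants and on reading completion as finishing the 30 weeks. If dropouts were replaced until 100 had completed, the review would still fall at the end, and more than the planned 100 would have been randomised.

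The loss is confined to one specified safeguard: the look at adverse events and urine results by unlabelled group that is meant to inform early ending for safety. It should be corrected because it is a decision threshold that fails if obeyed.

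**What to change.** Reconcile the panel paragraph in Section 7 with Section 6 by resetting the trigger to half of the amended sample. There are two workable forms:

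- **50 randomised participants.** This fits the description as the mid-point of enrolment, and dropout after randomisation cannot delay it. The price is shorter follow-up in those most recently randomised.
- **50 completers.** This gives full follow-up in those counted but falls after mid-enrolment, as Step 4 shows. If it is chosen, define completion.

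I would take the first. Keep the report of adverse events and urine results by group A and B. Because Section 6 now pools the two former studies, state whether the further split by study assignment stays; 50 participants over four cells is about 12 per cell (50 / 4 = 12.5), so the overall A-against-B comparison should lead.

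The cost is one line of protocol text, or two if the split is clarified, submitted as an amendment. The panel and the report are already planned, and neither the sample size nor the primary analysis changes.

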well as any necessary covariates, including cocaine positive vs negative urine tests prior to random assignment as a covariate. Generalized linear mixed models (GLMM) will be used to analyze repeated measures data, since this technique can include participants with incomplete data without resorting to imputation. This approach has been found to minimize bias and maximize power in cases of incomplete follow-up (see Hedden et al, 2009). Data will then be examined using the nonbinary method described by McCann and Li (2012) in which participants who meet an end of study threshold of success (1 week EOS abstinence) are assigned values indicating their number of beyond threshold weeks of success (in our case 1-24). This distribution will be analyzed as a function of drug condition using a two-sided Vander Waerden two-sample test (Permutt and Berger, 2000).

All other analyses will be conducted in the overarching group that includes those abstinent and actively using at baseline. This approach will allow us to preserve all study Aims with a reduced sample size that will ensure the study can be completed in the time allowed.

The data analysis plan consists of the following:

- 1) Comparison of groups for baseline differences. Participants will be compared as a function of medication group on baseline characteristics to determine whether they are comparable with respect to general demographic features, baseline drug use, and reinforcement measures (drug vs. money relative reinforcing potency scale, Snaith-Hamilton Pleasure scale). Groups will be compared using t tests for continuous measures and chi-square tests for categorical characteristics. If medication groups are found to differ on baseline measures, then these characteristics will be used as covariates in subsequent analyses assessing treatment effect.
 - 2) Primary outcome analyses: (see above)
- 3) Secondary outcome analyses: The main secondary outcome measure will be biochemically-confirmed abstinence from opiates. We hypothesize that participants receiving bupropion will have a higher proportion of opiate abstinent samples as well as for cocaine. Analyses conducted to assess the treatment effect for opiate use will be identical to those used for cocaine use (described above).

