In addition, study participants will receive periodic (e.g. every 6 weeks) assessment, for the presence of inter current health problems and for new concurrent medications that may pose a risk of drug-drug interactions. No specific laboratory monitoring is recommended for patients on bupropion. Participants will not be allowed to take any other antidepressants while they are on the study and will be discharged from the study if they need to begin taking any excluded medications that pose a risk of drug-drug interaction.

Experienced research, counseling, nursing, and medical staff will be readily available on-site as needed to assess and manage AE's and SAE's and research staff will be trained to report any responses indicating risk to medical and/or nursing personnel immediately for review and follow-up. Medical staff will evaluate participants who report clinically significant side effects possibly related to Bupropion (e.g., headache, agitation, insomnia) or who experience neuropsychiatric symptoms (e.g. depression, agitation). A code to break the drug blinds is available 24/7 if needed in response to a medical emergency. A participant may be put on close monitoring and/or referred for treatment if warranted in the judgment of medical staff. A participant may also be promptly withdrawn from the study protocol if medical staff indicates it is in the best interest of the patient. In all cases of persistent complaints, referral or study withdrawal, the case will be followed by medical staff until the complaint is resolved and the incident will be fully documented in study records and reported to IRB and NIDA.

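### The safety panel receives masked A vs B tables with no stated way to learn which group is bupropion, so it can see an imbalance but not its direction

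*Combined protocol and SAP*

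**What the plan says.** Risks Management in section 7 states that "an independent panel of consultants will be contracted for bi-annual review of the risks-benefits ratio of the study". One data review is described in detail. It falls "At mid-point during enrollment (when 100 randomized participants have completed the study", and the panel then gets adverse event reports and urine results "by unlabeled medication groups (A vs. B), as a function of study assignment (relapse prevention vs abstinence initiation". The panel is to judge "whether the risks reported are considered to be of unusual magnitude or frequency across any specific groups" and to decide whether the study should end early on safety grounds. No test, significance level or threshold is attached. The plan adds its own expectation: "It is unlikely that such a small study would be interrupted because of an uneven distribution of adverse events experienced by any one group".

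No other by-group table for the panel is described, and nothing says whether or how the panel may learn the identity of A and B. The one unblinding provision, earlier in the same part of section 7, reads "A code to break the drug blinds is available 24/7 if needed in response to a medical emergency". Section 4c applies the blind to research and counseling staff who deal with participants, so that their contact is not biased. It does not mention the panel.

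Section 6 now describes one study of 100 people, 50 per medication group, with the primary outcome modelled across everyone. It continues: "All other analyses will be conducted in the overarching group that includes those abstinent and actively using at baseline".

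**The concern.** The panel's remit is "bi-annual review of the risks-benefits ratio of the study". That is a signed question: does bupropion bring more harm or less, and more abstinence or less? A table headed A and B answers only the unsigned question of whether the groups differ.

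Suppose group B shows more adverse events and fewer cocaine-negative urines. If B is bupropion, the drug looks harmful on both counts. If B is placebo, the drug looks favorable on both counts, and the excess may reflect continued cocaine use. These readings point to opposite decisions. A panel that follows the plan as written has no stated means of telling them apart. It could let a harmful arm run on, or end a study in which the drug arm is doing better.

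The layout is a lesser matter. Showing the groups only within relapse prevention and abstinence initiation fits the superseded two-study design better than the single study in section 6.

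**Working it through.** **1. The plan's own figure.** The review is placed at the mid-point of enrollment, given as 100 completers. Mid-point = N/2. With the superseded total (section 6), 200/2 = 100, which matches. With the current total, 100/2 = 50, which does not. The stated trigger therefore equals the whole current sample. This is a timing matter, separate from what the panel sees.

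**2. What masking hides.** Take illustrative counts (assumed) of 5/50 with an event in A and 15/50 in B.
- Size of the imbalance: |15/50 − 5/50| = |0.30 − 0.10| = 0.20. This, and any two-sided p-value, is the same under either labeling.
- Bupropion minus placebo: +0.20 if B is bupropion, −0.20 if A is bupropion.

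The presence of a difference survives masking; its sign does not. The same holds for the urine results.

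**3. Cells in the panel table.** Section 6 gives 50 per medication group. Section 4 (Stratification and Random Assignment) expects close to an even split between responders and non-responders. Cells = 100/(2 × 2) = 25. Each medication group is then 25 + 25 = 50, so pooled totals can be obtained by adding cells that carry the same A and B labels.

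**4. Does the split lose information?** The documents give no event rates, test or significance level for this review, so the rates and the two-sided 0.05 level are assumptions. Exact power is the sum over all (a, b) of Bin(a; n, p1) × Bin(b; n, p2), counting only outcomes with Fisher p ≤ 0.05. The normal approximation is the reference for a Mantel-Haenszel test on the four cells (simulated, 200,000 replicates, no continuity correction).

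| Assumed rates | Fisher, one assignment (25 vs 25) | Fisher, pooled (50 vs 50) | Normal approx., pooled | Mantel-Haenszel, four cells |
|---|---|---|---|---|
| 5% vs 15% | 0.072 | 0.244 | 0.383 | 0.390 |
| 10% vs 20% | 0.086 | 0.195 | 0.286 | not run |
| 10% vs 25% | 0.180 | 0.410 | 0.506 | 0.510 |
| 10% vs 30% | 0.305 | 0.640 | 0.711 | 0.725 |
| 20% vs 40% | 0.231 | 0.515 | 0.590 | 0.596 |

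Reading one assignment alone is weak. A stratified reading of the same four cells gives back the pooled power (0.725 against 0.711 for 10% vs 30%), so the layout discards nothing.

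**5. What limits detection.** Even pooled, exact power is 20% for 10% vs 20% and 64% for 10% vs 30%. If the review took place at 50 people, the pooled comparison would be 25 vs 25, and these would fall to 9% and 31% (the 25 vs 25 column). Total size is the main limit. Labeling the groups changes none of these two-sided figures.

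**The case against.** Coded A/B reporting is a legitimate design choice: it keeps the panel even-handed until a question arises. The documents neither grant nor forbid unmasking of the panel. The emergency code concerns individual participants, so it should not be read as a limit on the panel. Nor are the tables the only protection. Section 7 also describes on-site medical evaluation and withdrawal, prompt written notice of serious adverse events to the IRB, and semi-annual adverse event summaries. All of this stands. However, none of those safeguards is described as a comparison of labeled arms, and silence on access to the key leaves the panel without a stated procedure when direction matters.

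Showing the two assignments is also defensible. Randomization is stratified by them, medication starts at different times (week 3 at the earliest, against week 6), the incentive schedules differ, and aims a and b still address the groups separately. That supports keeping the rows, though not omitting the totals.

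A reader might infer that the four-way split itself makes harm easy to miss. The documents do not support this. They require no test within an assignment, the cells add up, and a stratified reading recovers the pooled power. Nor did the cut from 200 to 100 thin these cells: the stated trigger was 100 completers, about 25 per cell, under either total. A reader might also infer that masking causes an excess to be overlooked. It does not; it hides only which arm has the excess.

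**Conclusion.** The point holds in a narrow form. As written, a panel charged with weighing risk against benefit and with the safety stop sees that A and B differ but has no stated means of learning which is bupropion. The consequence is a reversal of sign, not a loss of power: the same 0.20 difference is harm under one labeling and an advantage for bupropion under the other. This rests on the text alone and needs no assumed rates.

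The missing pooled totals are a display issue. The power figures rest on assumed rates and an assumed 0.05 level. They serve only to show that pooled presentation does not cure small numbers.

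The practical value of the fix depends on the trigger. At 100 completers out of a planned 100, nobody remains in the study for the review to protect, and any dropout means that count is never reached. This must be reconciled as well.

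**What to change.** In the independent-panel paragraph of Risks Management (section 7):

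1. State that the pharmacy gives the panel a sealed group key. The panel may open it in closed session, at its own request, when it judges an A vs B imbalance relevant to a decision to stop or continue. A bare rule of opening it whenever A and B differ would not do, since two groups nearly always differ to some extent. Investigators, counselors and research staff stay blinded.
2. Show pooled A vs B totals first, for adverse events and urine results, with the two assignments beneath. This makes the pooled reading explicit and matches section 6.
3. As a separate correction, reconcile the review trigger with the current total of 100.

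The first two changes cost a sealed key and one summary table, and need no new data. The small downside is that panel members who open the key are unmasked; the plan gives them no part in treating participants or collecting outcomes.
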